4. LIST OF ABBREVIATIONS AND DEFINITIONS OF TERMS

The following abbreviations and specialist terms are used in this study protocol.

Table 2: Abbreviations and Specialist Terms

Abbreviation or Specialist Term	Explanation
AE	Adverse event
ALP	Alkaline phosphatase
ALT	Alanine aminotransferase
AST	Aspartate aminotransferase
ATP	Adenosine triphosphate
ATS	American Thoracic Society
AUC	Area under the concentration-time curve
BMI	Body mass index
BP	Blood Pressure
BUN	Blood urea nitrogen
CFR	Code of Federal Regulations (US)
CK	Creatine kinase
CKD	Chronic kidney disease
C_{max}	Maximum drug concentration in plasma
CT	Computed tomography
DSMB	Data safety monitoring board
EC	Ethics Committee
eCRF	Electronic case report form
ECG	Electrocardiogram
EDC	Electronic data capture
eGFR	Estimated glomerular filtration rate
FDA	Food and Drug Administration (US)
GCP	Good Clinical Practice
GGT	Gamma-glutamyl transpeptidase
HCV	Hepatitis C virus
Hgb	Hemoglobin
ICH	International Conference on Harmonization
INR	International normalized ratio
IRB	Institutional Review Board

Abbreviation or Specialist Term	Explanation
IWRS	Interactive Web Response System
ITT	Intent-to-treat
LDH	Lactate dehydrogenase
MAR	Missing at random
MCH	Mean corpuscular hemoglobin
MCHC	Mean corpuscular hemoglobin concentration
MCV	Mean corpuscular volume
MMRM	Mixed model repeated measures
PK	Pharmacokinetic
RBC	Red blood cell
ROS	Reactive oxygen species
SAE	Serious adverse event
SAP	Statistical analysis plan
SF-36	36-item short form survey
SRC	Sample size re-calculation committee
TBL	Total bilirubin
T _{max}	Time when maximum drug concentration in plasma is achieved
ULN	Upper limit of normal
US	United States
WBC	White blood cell
WHO	World Health Organization
WOCBP	Women of child bearing potential

5. INTRODUCTION

New major epidemic foci of coronavirus disease 2019 (COVID-19), have been identified and are rapidly expanding in Europe, North America, Asia, and the Middle East, with the first confirmed cases being identified in African and Latin American countries.¹ By March 16, 2020, the number of cases of COVID-19 outside China had increased drastically and the number of affected countries, states, or territories reporting infections to WHO was 143.1 On the basis of “alarming levels of spread and severity, and by the alarming levels of inaction”, on March 11, 2020, the Director-General of WHO characterized the COVID-19 situation as a pandemic.

The WHO Strategic and Technical Advisory Group for Infectious Hazards (STAG-IH) regularly reviews and updates its risk assessment of COVID-19 to make recommendations to the WHO health emergencies programme.² STAG-IH's most recent formal meeting on March 12, 2020, included an update of the global COVID-19 situation and an overview of the research priorities established by the WHO Research and Development Blueprint Scientific Advisory Group that met on March 2, 2020, in Geneva, Switzerland, to prioritize the recommendations of an earlier meeting on COVID-19 research held in early February, 2020.

To respond to COVID-19, many countries are using a combination of containment and mitigation activities with the intention of delaying major surges of patients and levelling the demand for hospital beds, while protecting the most vulnerable from infection, including elderly people and those with comorbidities. Activities to accomplish these goals vary and are based on national risk assessments that many times include estimated numbers of patients requiring hospitalization and availability of hospital beds and ventilation support. Most national response strategies include varying levels of contact tracing and self-isolation or quarantine; promotion of public health measures, including handwashing, respiratory etiquette, and social distancing; preparation of health systems for a surge of severely ill patients who require isolation, oxygen, and mechanical ventilation; strengthening health facility infection prevention and control, with special attention to nursing home facilities; and postponement or cancellation of large-scale public gatherings.

Based on more than 500 genetic sequences submitted to GISAID (the Global Initiative on Sharing All Influenza Data), the virus has not drifted to significant strain difference and changes in sequence are minimal. There is no evidence to link sequence information with transmissibility or virulence of severe acute respiratory syndrome coronavirus 2 (SARS-CoV-2), the virus that causes COVID-19.

SARS-CoV-2, like other emerging high-threat pathogens, has infected health-care workers in China and several other countries. To date, however, in China, where infection prevention and control was taken seriously, nosocomial transmission has not been a major amplifier of transmission in this epidemic. Epidemiological records in China suggest that up to 85% of human-to-human transmission has occurred in family clusters and that 2055 health-care workers have become infected, demonstrating that patient to healthcare worker is tractable. However, there have been no major nosocomial outbreaks and some supporting evidence that some health-care workers may have acquired infection or transmitted the infection to their families. These findings suggest that close and unprotected exposure is required for transmission by direct contact or by contact with fomites in the immediate environment of those with infection. Continuing reports from outside China suggest the same means of transmission to close contacts

and persons who attended the same social events or were in circumscribed areas such as office spaces or cruise ships. It has been suggested that a healthcare worker that had 15-30 min of exposure within 6 feet of an infected patient without PEP could acquire the infection.

Intensified case finding and contact tracing are considered crucial by most countries and are being undertaken to attempt to locate cases and to stop onward transmission. Confirmation of infection at present consists of PCR for acute infection, and although many serological tests to identify convalescent antibodies which confer potential immunity are being developed they require validation with well characterized sera before they are reliable for general use.

From studies of viral shedding in patients with mild and more severe infections, shedding seems to be greatest during the early phase of disease. The role, if any, of asymptomatic carriers in transmitting infection is not yet completely understood. Pre-symptomatic infectiousness is a concern among healthcare workers and many countries are now using 1–2 days of symptom onset as the start day for contact identification.

A comprehensive report published by the Chinese Center for Disease Control and Prevention on the epidemiological characteristics of 72,314 patients with COVID-19 confirmed previous understanding that most known infections cause mild disease, with a case fatality ratio that ranged from 2.9% in Hubei province to 0.4% in the other Chinese provinces. This report also suggested that elderly people, particularly those older than 80 years, and people with comorbidities, such as cardiac disease, respiratory disease, and diabetes, are at greatest risk of serious disease and death. The case definition used in China changed several times as COVID-19 progressed, making it difficult to completely characterize the natural history of infection, including the mortality ratio. Information on mortality and contributing factors from outbreak sites in other countries varies greatly, and seems to be influenced by such factors as age of patients, associated comorbidities, availability of isolation facilities for acute care for patients who need respiratory support, and surge capacity of the health-care system. Individuals in care facilities for older people are at particular risk of serious disease as shown in the report of a series of deaths in an elderly care facility in Washington State.

The pandemic of COVID-19 has clearly entered a new stage with rapid spread in countries outside China and all members of society must understand and practice measures for self-protection and for prevention of transmission of infection to others. STAG-IH makes the following recommendations.

First, countries need to rapidly and robustly increase their preparedness, readiness, and response actions based on their national risk assessment and the four WHO transmission scenarios for countries with no cases, first cases, first clusters, and community transmission and spread (4Cs).

Second, all countries should consider a combination of response measures: case and contact finding; containment or other measures that aim to delay the onset of patient surges where feasible; and measures such as public awareness, promotion of personal protective hygiene, preparation of health systems for a surge of severely ill patients, stronger infection prevention and control in health facilities, nursing homes, and long-term care facilities, and postponement or cancellation of large-scale public gatherings.

Third, countries with no or a few first cases of COVID-19 should consider active surveillance for timely case finding; isolate, test, and trace every contact in containment; practice social distancing; and ready their health-care systems and populations for spread of infection.

[figure not shown]
None of these suggested by STAG-IH address the issue of healthcare workers with concern over high-risk exposures such as those who would qualify for this trial.

Azithromycin may have direct and indirect antiviral effects on human cells infected with pathogenic strains of viruses that could apply in COVID-19 infection.^{3 4 5 6 7 8}

Hydroxychloroquine and chloroquine are antimalarial agents that have been used for decades for both active treatment and prophylaxis. Several sources of data and rationale have been developed to support the notion that hydroxychloroquine may have activity against COVID-19.^{9 10 11 12 13}

[figure not shown]
A prospective open-label trial from France evaluated the efficacy of hydroxychloroquine alone and in combination with azithromycin in symptomatic, hospitalized patients with positive COVID-19. The study composed of 36 patients, out of which 20 received 600 mg of hydroxychloroquine daily for 10 days. The remaining 16 patients who either refused the treatment or were not eligible to receive it because they were at other centers in France were considered as the control group. The primary endpoint was virological clearance of NP sampling at six days. Six patients who received hydroxychloroquine contributed incomplete NP sampling to the analysis because three worsened and were transferred to the intensive care unit, one patient died, one patient left the hospital, and one patient could not tolerate the study medication due to nausea. At day 6, 70% of hydroxychloroquine-treated patients were virologically cured comparing with 12.5% in the control group ($p= 0.001$). The investigators found the rate of recovery in patients taking hydroxychloroquine to be approximately 5 times more than that of patients in the control group. Six patients were additionally treated with Azithromycin for presumed superimposed bacterial infection. The figure below, demonstrates the efficacy of hydroxychloroquine alone and in combination with azithromycin according to the French study¹⁴:

Figure 2. Percentage of patients with PCR-positive nasopharyngeal samples from inclusion to day6 post-inclusion in COVID-19 patients treated with hydroxychloroquine only, in COVID-19 patients treated with hydroxychloroquine and azithromycin combination, and in COVID-19 control patients.

Please cite this work as Gautret et al. (2020) Hydroxychloroquine and azithromycin as a treatment of COVID-19: results of an open-label non-randomized clinical trial. International Journal of Antimicrobial Agents – In Press 17 March 2020 – DOI : 10.1016/j.ijantimicag.2020.105949

Finally, research gaps about COVID-19 should be addressed in prospective, clinical trials as proposed in this study. The present study will leverage information concerning the infectious curve associated with COVID-19 exposure as illustrated in the figure.

5.1. Clinical Experience with Hydroxychloroquine

Please refer to the package insert.

5.1.1. Safety and Tolerability

Please refer to the package insert for a detailed discussion of safety findings for studies in healthy subjects, rheumatology, infectious diseases, and other illnesses patients with hydroxychloroquine.

5.1.2. Clinical Experience with hydroxychloroquine

Please refer to the package insert for a detailed discussion of clinical experience and efficacy findings for studies in healthy subjects, rheumatology, infectious diseases, and patients with other illnesses

5.1.3. Transaminase and GGT Elevations

In clinical studies of hydroxychloroquine, patients may have increases of transaminase enzymes above baseline upon initiation of treatment, please refer to the package insert for a detailed discussion.

5.1.4. Muscle Discomfort

In clinical studies of hydroxychloroquine, patients may have increases in muscle discomfort above baseline upon initiation of treatment, please refer to the package insert for a detailed discussion.

5.1.5. Anemia

Clinical studies of hydroxychloroquine, patients may have reductions in hemoglobin from baseline upon initiation of treatment, please refer to the package insert for a detailed discussion.

5.1.6. Prolonged QT and Risk for Arrhythmias

Hydroxychloroquine may prolong the QT interval. Please refer to the package insert for a detailed discussions.

6. STUDY OBJECTIVES AND ENDPOINTS

6.1. Objectives

For healthcare workers with

- One day or more of exposure to suspected and/or positive COVID-19 patients, including but not limited to those working in the Emergency Department or Intensive Care Unit.

OR

- Unprotected exposure to a known positive COVID-19 patient within 72 hours of screening.

6.1.1. Primary Objective

To assess the efficacy of hydroxychloroquine 400 mg twice a day (two 200 mg tablets twice a day) on day 1 followed by two 200 mg tablets once a week for a total of 7 weeks in the prevention of COVID-19 infection

6.1.2. Secondary Objective

To compare the rate of COVID-19 positive conversion among emergency department workers versus intensive care unit workers

6.2. Endpoints

6.2.1. Primary Efficacy Endpoint

Rate of COVID-19 positive conversion on weekly nasopharyngeal (NP) sampling

6.2.2. Secondary Efficacy Endpoints

Time-to-first clinical event consisting of a persistent change for any of the following:

- One positive NP sample
- Common clinical symptoms of COVID-19 infection including fever, cough, and shortness of breath
- Less common signs and symptoms of COVID-19 infection including headache, muscle pain, abdominal pain, sputum production, and sore throat

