This prospective open label trial will study the safety, tolerability, and efficacy of hydroxychloroquine 400 mg po in qualified health care workers.

Qualified individuals will be prescribed oral hydroxychloroquine 400 mg twice a day (two 200 mg tablets twice a day) on day 1 followed by two 200 mg tablets once a week for a total of 7 weeks. Dose de-escalation is permitted during the study if indicated clinically. Please refer to [Section 7.3.1](#) for additional details on dose escalation and dose de-escalation.

All study individuals will follow the same visit and assessment schedule. Following study recruitment, participants will be scheduled to be assessed in person during treatment at days 7, 14, 21, 28, 35, 42 and 49.

Healthcare workers who are qualified for the trial but decline participation in receiving the treatment will form the control group and will be offered an observational registry where the same NP COVID-19 sampling schedule and other assessments will be followed with the exception of blood testing. The clinical outcomes will be captured in the same manner and with the same definitions as the clinical arm.

Number of Subjects (planned):

360 individuals will be enrolled into the study with half enrolling in the active treatment study and the other half, those who refuse to get the study treatment, will be entering an observational registry considered as the control group.

Main criteria for inclusion:

1. Adult male and female healthcare workers ≥ 18 to ≤ 75 years of age upon study consent
2. Healthcare workers with
 - One day or more of exposure to suspected and/or positive COVID-19 patients, including but not limited to those working in the Emergency Department or Intensive Care Unit.OR
 - Unprotected exposure to a known positive COVID-19 patient within 72 hours of screening.
3. Afebrile with no constitutional symptoms
4. Willing and able to comply with scheduled visits, treatment plan, and other study procedures
5. Evidence of a personally signed and dated informed consent document indicating that the subject (or a legally acceptable representative) has been informed of all pertinent aspects of the study prior to initiation of any subject-mandated procedures

Major exclusion criteria:

1. Participation in other investigational clinical trials for the treatment or prevention of SARS-COV-2 infection within 30days

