7.5. Schedule of Assessments

[Table 3](#) lists the overall schedule of assessments for the study.

Table 3: Schedule of Assessments

Assessment	Study Day (Day)	Screen A ^a	Day 1 ^b	Day 7 Day 7±3	Day 14 Day 14±3	Day 21 Day 21±3	Day 28 Day 28±3	Day 35 Day 35±3	Day 42 Day 42±3	Day 49 ^j Day 49±3 (End of study visit)
Informed consent		X								
Inclusion/ exclusion		X	X ^c							
Self-reported Pregnancy Status ^d		X	X	X	X	X	X	X	X	X
Demographics and baseline disease characteristics		X								
Prior and Concomitant medications		X	X	X	X	X	X	X	X	X
Current background medications		X	X	X	X	X	X	X	X	X
Medical history		X								
Self-reported Height		X								
Self-reported Weight		X								
Body temperature		X	X	X	X	X	X	X	X	X
Study drug administration			X	X	X	X	X	X	X	
Dispense study drug ^e			X	X	X	X	X	X	X	
Collect study drug ^f				X	X	X	X	X	X	X
nasopharyngeal (NP) sampling			X	X	X	X	X	X	X	X
Adverse event collection			X ^g	X	X	X	X	X	X	X
Visual analogue scale (VAS) for cough severity		X	X	X	X	X	X	X	X	X
Exposure assessment		X	X	X	X	X	X	X	X	X
Virus serology ^h		X			X		X		X ⁱ	

^a Total Screening period should not exceed 30 days. Screening and Day 1 can be completed in the same visit.

^b Day 1 is the day of administration of the first dose. **On Day 1, all procedures should be performed before study drug administration.**

^c Screening eligibility procedures do not need to be repeated on Day 1; however, a review of any changes in eligibility criteria should be evaluated prior to Day 1 procedures

^d Female participants will be asked with respect to their pregnancy as a verbal check

^e Depending on the availability of the drug supply, the schedule of drug dispensing might change

^f If the schedule for drug dispensing changes, the arrangements for drug collection will change accordingly

^g AE assessments on Day 1 should be performed following study drug administration

^h Only applicable to those who choose to participate in the optional viral serology study

ⁱ Individuals who terminate from the study prior to the Day 49 study visit should return to the clinic as soon as possible for early termination assessments (*i.e.*, Day 49 Day Prior and end-of-treatment visits). Participants should complete the end-of-treatment procedures, including assessments, prior to any adjustments being made to their treatment regimen.

^j If final serology draw not collected at Day 42, it can be collected at day 49

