9.8.11. Cough Visual Analog Scale

Cough visual analogue scale (VAS, 0–100 mm) will be recorded as indicated in [Table 3](#) to assess cough severity in patients with chronic cough. Please refer to appendix II for cough visual analogue scale template.

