11.2. Adverse and Serious Adverse Events

11.2.1. Definition of Adverse Events

11.2.1.1. Adverse Event

An adverse event (AE) is defined as any untoward medical occurrence in a subject regardless of its causal relationship to study drug. An AE can be any unfavorable and unintended sign (including any clinically significant abnormal laboratory test result), symptom, or disease temporally associated with the use of the study drug, whether or not it is considered to be study-drug related. Included in this definition are any newly-occurring events or previous condition that has increased in severity or frequency since the administration of study drug.

All AEs that are observed or reported by the subject during the study (from time of administration of the first dose at the Day 1 visit until the final visit indicated in [Table 3](#) must be reported, regardless of their relationship to study drug or their clinical significance.

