Each AE should be recorded to represent a single diagnosis. Accompanying signs (including abnormal laboratory test values or ECG findings) or symptoms should NOT be recorded as additional AEs. If a diagnosis is unknown, sign(s) or symptom(s) should be recorded as an AE(s). Changes in laboratory test values are only considered AEs if they are judged to be clinically significant (*i.e.*, if some action or intervention is required or if the investigator judges the change to be beyond the range of normal physiological fluctuation). If abnormal laboratory test values are the result of pathology for which there is an overall diagnosis (*e.g.*, increased creatinine levels in renal failure), only the diagnosis should be reported as an AE.

Elective procedures (surgeries or therapies) that were scheduled prior to the start of AE collection are not considered AEs. These elective procedures should not be recorded as AEs, but should be documented in the subject’s source documents as elective (*e.g.*, elective periodontal surgery). However, if a pre-planned procedure is performed early (*e.g.*, as an emergency) because of a worsening of the preexisting condition, the worsening of the condition should be captured as an AE.

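### Six of the eight symptoms in the secondary endpoint have no scheduled measure, and the adverse-event route left to them has no clear start point for undosed controls

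*Protocol*

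**What the plan says.** Protocol 6.2.2 defines the only secondary efficacy endpoint as "Time-to-first clinical event consisting of a persistent change for any of the following". The components are a positive nasopharyngeal swab, then "Common clinical symptoms of COVID-19 infection including fever, cough, and shortness of breath", then "Less common signs and symptoms of COVID-19 infection including headache, muscle pain, abdominal pain, sputum production, and sore throat". SAP 4.2 repeats this and adds no derivation rule. Neither document says what makes a change persistent.

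**Scheduled measures.** Table 3 (section 7.5) has rows for body temperature and a cough visual analogue scale, both at screening, Day 1 and every visit to Day 49. Section 9.8.11 gives the purpose of the scale as "to assess cough severity in patients with chronic cough". Section 9.8 describes no symptom diary or checklist, and the Appendix III questionnaire covers exposure only.

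**Adverse events.** Sections 9.8.16 and 11.3 rely on staff observation and a non-directed question about how the subject has felt. Section 11.2.1.1 sets the reporting period as "from time of administration of the first dose at the Day 1 visit until the final visit". A Table 3 footnote adds: "AE assessments on Day 1 should be performed following study drug administration". Section 11.6 asks for one diagnosis per event and states: "Accompanying signs (including abnormal laboratory test values or ECG findings) or symptoms should NOT be recorded as additional AEs". Its next sentence has symptoms recorded as events when the diagnosis is not known.

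**Controls.** Under section 7.3 they are the people who opt out of treatment. The synopsis (Methodology) gives them the same swab schedule and other assessments apart from blood tests, and says: "The clinical outcomes will be captured in the same manner and with the same definitions as the clinical arm". Section 7.1 and Appendix I say much the same.

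**The concern.** A time-to-first-event composite is only as sound as its least well captured component. If a symptom is recorded more readily in one group, that group shows more and earlier events even when the drug does nothing. Here participants choose their group and know what they take, so self-reported symptoms are already exposed to reporting differences. Routing most of them through drug-safety reporting adds to that, because its start is defined by an act that controls never perform. Section 5.1.4 also notes that muscle discomfort may increase on hydroxychloroquine, so a tolerability complaint can look like an endpoint component.

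This goes beyond a gap in the SAP. Symptoms that nobody asked about at the visit cannot be reliably recovered at analysis.

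**Working it through.** The plan states no figure on this point, so there is none to reproduce. The check sets the endpoint against the assessment schedule.

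**Step 1: components against scheduled measures.**

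| Symptom in 6.2.2 | Scheduled measure in Table 3 |
|---|---|
| Fever | Body temperature |
| Cough | Cough scale (9.8.11: chronic cough) |
| Shortness of breath | None |
| Sore throat | None |
| Sputum production | None |
| Headache | None |
| Abdominal pain | None |
| Muscle pain | None |

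Eight symptoms less two with a measure leaves six; 6/8 = 75%. Counting cough as measured is generous, given the stated scope of the scale.

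**Step 2: can adverse-event collection fill the gap?**

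- *Method.* The question is open, so it does not ask about each symptom.
- *Start.* Sections 9.8.16, 11.2.1.1 and 11.6 all refer to the first dose. Section 7.3 means controls have none. The synopsis, section 7.1 and Appendix I promise controls equal assessment but name neither an instrument nor a start point.
- *Recording.* The single-diagnosis rule in 11.6 keeps accompanying symptoms from being listed as additional events. Symptoms with no known diagnosis are recorded, and section 11.6 requires an onset date for each event. A swab-confirmed case already counts through the swab component. The rule therefore bears mainly on event dating and on symptoms absorbed into other diagnoses.
- *Baseline.* Section 8.1 requires entrants to be free of fever and constitutional symptoms. Temperature and the cough scale are taken before the first dose, and prior conditions go to medical history. The baseline is partial, with no symptom-by-symptom record.

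**Step 3: what unequal capture could do.** The inputs here are assumptions, not figures from the documents for this endpoint. They are: no drug effect; a 30% risk of a positive swab, fever or cough in both groups; a true risk q of any of the six symptoms, equal in both groups; independent components; proportional hazards; and capture of 80% on drug against c in controls.

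- Treated event risk: P_T = 1 − 0.70 × (1 − 0.80q)
- Control event risk: P_C = 1 − 0.70 × (1 − cq)
- Apparent hazard ratio, treated versus control: ln(1 − P_T) / ln(1 − P_C)

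Example with q = 0.4 and c = 0.6: P_T = 1 − 0.70 × 0.68 = 0.524; P_C = 1 − 0.70 × 0.76 = 0.468; ratio = ln(0.476)/ln(0.532) = 1.18.

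| Control capture c | q = 0.2 | q = 0.4 | q = 0.6 |
|---|---|---|---|
| 80% (equal) | 1.00 | 1.00 | 1.00 |
| 60% | 1.10 | 1.18 | 1.26 |
| 40% | 1.21 | 1.40 | 1.60 |
| 0% | 1.49 | 2.08 | 2.83 |

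Equal capture gives no distortion. A moderate shortfall in controls is enough to create a difference from nothing, and a shortfall on drug would distort the comparison the other way.

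**The case against.** The strongest reply is that the plan does cover controls. Adverse-event collection is a Table 3 assessment, blood testing is the only stated exception for controls, and section 11.3 asks its question at every study visit without mentioning a dose. This stands, and it rules out several stronger readings.

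- *That controls have zero days of symptom collection against about 49 on drug.* A reader might infer this from the first-dose wording. The documents do not exclude controls; they make two statements that have not been reconciled.
- *That the single-diagnosis rule loses the onset dates of symptomatic COVID-19 in both groups.* Section 11.6 records symptoms when the diagnosis is unknown and asks for onset dates, and responses also go into source documents.
- *That there is no pre-dose status from which to judge change.* The eligibility criteria, temperature, cough scale and medical history supply part of it.
- *That bias must show more and earlier events on drug.* That requires lower capture in controls, which the documents do not establish. The 0% row above is an extreme case, not an estimate.

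The case report form is also unavailable, and it might hold a symptom page. Even so, neither Table 3 nor the SAP refers to one, and none of these replies supplies a scheduled measure for the six symptoms.

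**Conclusion.** The point holds in a limited form. Six of the eight symptom components have no scheduled measure in either group, and the one route left to them has an ambiguous start for controls. Symptom ascertainment may be incomplete and may differ between groups.

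The count of six follows directly from the documents. The hazard ratios of 1.10 to 1.26 at 60% control capture, and up to 2.83 at none, rest wholly on the assumed inputs and show only that unequal capture matters. The actual size and direction depend on how controls are questioned in practice and on a case report form that cannot be seen.

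The primary endpoint and the sample size rest on swab results and are untouched. Because only a secondary composite is affected, the point ranks below a must-fix.

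**What to change.** - Add a row to Table 3 for a dated checklist of the eight symptoms: yes or no, onset date and end date. Complete it before dosing on Day 1 (at enrolment for controls), at Days 7 to 49 and at any unscheduled visit under section 9.5, identically in both groups.
- Define persistent change in Protocol 6.2.2 and SAP 4.2. A checklist alone leaves the endpoint underivable.
- Derive the symptom components from the checklist rather than from adverse-event records.
- State in 9.8.11 that the cough scale applies to all subjects, as Table 3 implies.
- Reconcile the first-dose wording in 9.8.16, 11.2.1.1 and 11.6 with the synopsis, section 7.1 and Appendix I, so that controls have a stated start point.

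The cost is a few minutes at visits already held in person, plus a minor amendment. The checklist does not remove self-report bias in an open-label, self-selected comparison, nor the overlap between muscle pain as an endpoint and muscle discomfort as a drug effect. Results on this endpoint should be read with that in mind.
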